4.1 Inclusion Criteria

- 4.1.1** Newly diagnosed or previously treated subjects with KSHV-associated MCD that is pathologically confirmed by characteristic histologic features and latency-associated nuclear antigen (LANA) positivity by IHC.
- 4.1.2** Age ≥ 18 at time of consent.
- 4.1.3** Can provide informed consent.
- 4.1.4** HIV-infected or HIV-uninfected.
- 4.1.5** If HIV-infected, must be on or willing to start antiretroviral therapy including lamivudine or tenofovir.
- 4.1.6** Willing to comply with study visits.
- 4.1.7** MCD treatment indicated based on the presence of a symptomatic MCD flare, defined as the presence of each of the following three criteria:
 - 1. Fever (subjective or objective)
 - 2. Lymphadenopathy or hepatosplenomegaly
 - 3. At least one of the following signs or symptoms attributable to MCD by the local study investigator:
 - Weight loss $>5\%$
 - Malaise
 - Anemia (Hemoglobin <10 g/dL) within the past 4 weeks
 - Thrombocytopenia (Platelets $<100 \times 10^3/\mu\text{L}$)
 - Note that if only two of the three criteria are present, but the provider feels treatment is indicated for a symptomatic MCD flare, this will be allowed after communication with the study principle investigator (PI).
 - Note that subjects with low hemoglobin within the past 4 weeks that have since received a blood transfusion are still eligible for participation. The subject's

pre-transfusion hemoglobin value will be considered when determining risk classification.

4.1.8 Females of childbearing potential must have a negative urine pregnancy test within three days prior to registration.

- Note that females are considered of childbearing potential unless they are surgically sterile (have undergone a hysterectomy, bilateral tubal ligation, or bilateral oophorectomy) or they are naturally postmenopausal for at least 12 consecutive months. Documentation of postmenopausal status must be provided.

4.1.9 Females must agree to abstain from breast-feeding during therapy and for 6 months after the completion of therapy.

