5.0 TREATMENT PLAN

5.1 Schema

[figure not shown]

Figure 4. Clinical trial schema for newly diagnosed patients with MCD requiring treatment.
"High-risk disease" defined as ECOG performance status >2 or hemoglobin <8 g/dL.

Clinical trial schema for newly diagnosed patients with MCD requiring treatment.

¹ "High-risk disease" defined as ECOG performance status >2 or hemoglobin <8 g/dL at the time of screening or enrollment labs. Note that a patient receiving a blood transfusion due to hemoglobin <8 g/dL within 1 month of enrollment will be considered high-risk.

² See Time and Events Table (8.1) for detailed study visit components.

³ MCD-SS=MCD symptom score

We will conduct a single arm, phase II clinical trial for safety and efficacy of risk-stratified treatment with rituximab +/- chemotherapy for MCD. Eligible patients will be enrolled and treated according to the study schema. High-risk patients (defined as patients with ECOG performance status >2 or hemoglobin <8 g/dL at the time of screening or enrollment labs)^{9,10,13-16} will receive four weekly doses of rituximab (375 mg/m²) and etoposide (100 mg/m²) as in Bower, et al.⁹ Low-risk patients will receive the same dose of rituximab alone.

The planned sample size is 27 patients and the primary outcome is safety. Secondary outcomes include one- and two-year EFS (combination of relapse, development of NHL, or death), OS, and KS exacerbation rates.

We will also collect clinical, laboratory, virologic data, and stored samples at baseline and end-of-treatment to both describe the presentation of MCD in our population and to evaluate risk factors for death or relapse.

Finally, we will conduct comprehensive microcosting analysis and a Markov model cost-effectiveness analysis.

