8.0 EVALUATIONS AND ASSESSMENTS

8.1 Time and Events Table (Table 7)

Table 7: Time and Events Table.	Initial Visit or Relapse ¹	Treatment days 1, 8, 15, and 22 ²	End-of-treatment (Week 5)	Follow-up (12 weeks)	Long term follow up ⁴
Informed consent	Initial visit only				
History & physical exam ⁵	X	X	X	X	X
Concomitant medications ⁶	X	X	X		
ECOG performance status ⁷	X	X	X		
Toxicity evaluation ⁸	X	X	X	X	X ⁸
Tumor biopsy ⁹	X				
Survival ¹⁰		X	X	X	X
Treatments ¹¹		X			
Lymph node measurements	X	Day 15 only	X	X	X
MCD-SS and Quality of life assessment ¹²	X	Day 15 only	X	X	X ¹²
Chest X-ray and abdominal ultrasound	X		X ¹³		
Hematology & blood chemistries ¹⁴	X ¹⁵	X ¹⁶	X	CBC only	CBC only
Correlative blood samples ¹⁷	X	Day 15 only	X	X	X ¹⁹
Lactate dehydrogenase	X	Day 15 only	X		

Viral and host genotyping	X	
Urine pregnancy test	X ¹⁸	
Hepatitis B (for HIV-negative patients)	X	
CD4 and HIV RNA (if HIV positive)	X	X ¹⁹

¹ Screening assessments must be completed within 21 days prior to study enrollment.

² A window of +/- 7 days will apply to all study visits; however, lymph node measurements must take place prior to that cycle's treatment.

³ End-of-treatment visit should occur 7-14 days from final dose of chemotherapy. A subject who is being withdrawn for disease progression or for other reasons (e.g. unacceptable toxicity, etc.) should complete an end of treatment visit.

⁴ Long term follow-up will occur every 3 months until 24 months after the start of treatment unless otherwise noted.

⁵ After the initial visit (comprehensive history and physical exam) subsequent visits will address a focused history and physical exam.

⁶ All concomitant medications will be recorded.

⁷ See Appendix E. ECOG Performance Status

⁸ per NCI CTCAEv5.0 for notation of baseline toxicity. Assess from initial visit through first follow-up visit (12 weeks) and again at the final follow up visit (24 months).

⁹ Archival and/or fresh sample.

¹⁰ Survival will be assessed at each visit through out the duration of treatment, follow up, and long term follow up.

¹¹ Subjects with low risk disease will receive rituximab at 375 mg/m² weekly for 4 weeks. High risk subjects will receive rituximab at 375 mg/m² and etoposide at 100 mg/m² weekly for 4 weeks.

¹² Quality of life assessment includes PROMIS Global 10, MCD-SS and QoL will be assessed through follow up, and at 24 months during long term follow up. QoL will also be assessed at the time of any relapse.

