¹³ Omitted if no baseline abnormalities on chest x-ray and abdominal ultrasound.

¹⁴ Hematology assessments include hemoglobin, white blood cell count, white blood cell differential, and platelet count. Blood chemistry assessments include serum creatinine, total bilirubin, albumin, and the following as deemed necessary per SOC: sodium, potassium, chloride, bicarbonate, glucose, blood urea nitrogen, aspartate aminotransferase, alanine aminotransferase, and alkaline phosphatase. See the T&E table for when lactate dehydrogenase is measured.

¹⁵ If a patient has been tested for hemoglobin within 1 month of enrollment and received a blood transfusion due to low hemoglobin, then the original test will dictate treatment group (high vs low risk).

¹⁶ Hemoglobin and platelet count will be assessed per SOC during treatment.

¹⁷ Blood sample for correlates will include assessments of C-reactive protein, KSHV viral load from plasma and PBMCs, and cytokine levels (IL-6, IL-10, IL-2, TNF α , INF γ). KSHC genotyping will occur on the first draw only. Blood draws will be two 10 mL tubes (2 heparin tubes separated into plasma and PBMCs) and 1 tube (5 mL) with citrate. Correlative blood samples collected during long term follow up will be stored and analyzed

¹⁸ In women under 60 years of age, required within 3 days of start of treatment.

¹⁹ At 12 and 24 month long term follow up visits.

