10.0 STATISTICAL CONSIDERATIONS

10.1 Study Design/Study Endpoints

This is a single arm, prospective, phase II clinical trial for safety and efficacy of risk-stratified treatment with rituximab +/- chemotherapy for MCD. Eligible patients will be enrolled and treated according to the study schema. High-risk patients (defined as patients with ECOG performance status >2 or hemoglobin <8 g/dL during screening or enrollment)^{9,10,13-16} will receive four weekly doses of rituximab (375 mg/m²) and etoposide

(100 mg/m²) as in Bower, et al.⁹ Note that patients with low hemoglobin within the last month that receive a blood transfusion as treatment will be considered high risk if their pre-transfusion hemoglobin was <8 g/dL. Low-risk patients will receive the same dose of rituximab alone. The planned sample size is 27 patients and the primary outcome is safety. Secondary outcomes include one- and two-year EFS (relapse, development of NHL, or death), OS, and KS exacerbation rates. We will also collect clinical, laboratory, virologic data, and stored samples at baseline and end-of-treatment to both describe the presentation of MCD in our population and to evaluate risk factors for death or relapse. Finally, we will conduct comprehensive microcosting analysis and a Markov model cost-effectiveness analysis.

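### Footnote 15 of Table 7 and sections 5.1 and 10.1 give different risk groups, and so different regimens, to a patient transfused at 8 g/dL or above whose screening or enrollment hemoglobin is below 8 g/dL

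*Combined protocol and SAP*

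**What the plan says.** Four places in the combined protocol and SAP tell the site how to classify a patient who has had a recent transfusion.

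- **Section 5.1 (schema, footnote 1, and body text).** High-risk disease is "defined as ECOG performance status >2 or hemoglobin <8 g/dL at the time of screening or enrollment labs". The footnote adds: "Note that a patient receiving a blood transfusion due to hemoglobin <8 g/dL within 1 month of enrollment will be considered high-risk".
- **Section 10.1.** The same two criteria, with a note that a transfused patient "will be considered high risk if their pre-transfusion hemoglobin was <8 g/dL".
- **Section 4.1.7.** "Note that subjects with low hemoglobin within the past 4 weeks that have since received a blood transfusion are still eligible for participation". It then says that the patient's "pre-transfusion hemoglobin value will be considered when determining risk classification".
- **Section 8.1, Table 7, footnote 15.** Where a test in the month before enrollment was low and led to a transfusion, the rule is: "then the original test will dictate treatment group (high vs low risk". The footnote is attached to the initial-visit cell of the row "Hematology & blood chemistries ¹⁴". ECOG has its own row and its own footnote (7).

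The group fixes the regimen. Under section 5.1 and Table 7 footnote 11, high-risk patients receive rituximab plus etoposide and low-risk patients receive rituximab alone. Section 4.2.10 excludes ECOG above 3, so ECOG 3 is the only enrollable level that meets the ECOG criterion.

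**The concern.** The transfusion notes in 5.1 and 10.1 work in one direction. They move a patient into the high-risk group when the pre-transfusion hemoglobin was below 8 g/dL, and never move anyone out. Footnote 15 works in both directions: the original test settles whether the patient is high-risk or low-risk. It gives no threshold for low hemoglobin, so it also reaches patients transfused at 8 g/dL or above, for whom the original test points to low risk. Section 4.1.7 uses a weaker verb again, under which the earlier value is taken into account without being decisive.

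At stake is whether a patient is given etoposide. Section 11.4 requires the study to be run exactly as the protocol describes. For the affected patient, staff working from Table 7 and staff working from 5.1 cannot both comply.

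**Working it through.** The plan gives no figure on this point, so the check is a classification of every case.

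**Inputs.** All cases are patients transfused for low hemoglobin within the look-back period. *Pre* is the hemoglobin before transfusion, *current* is the screening or enrollment hemoglobin after it, and ECOG is 0–2 or 3. Each hemoglobin is either below 8 g/dL or at least 8 g/dL, so there are 2 × 2 × 2 = 8 combinations.

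**Rules.**

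- A (5.1 and 10.1): high-risk if ECOG >2, or current <8, or pre <8.
- B (footnote 15, read as choosing which hemoglobin value counts): high-risk if ECOG >2 or pre <8.
- C (footnote 15, read strictly literally): high-risk if pre <8.

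| Pre | Current | ECOG | A | B | C |
|---|---|---|---|---|---|
| <8 | <8 | 0–2 | High | High | High |
| <8 | <8 | 3 | High | High | High |
| <8 | ≥8 | 0–2 | High | High | High |
| <8 | ≥8 | 3 | High | High | High |
| ≥8 | <8 | 0–2 | High | **Low** | **Low** |
| ≥8 | <8 | 3 | High | High | **Low** |
| ≥8 | ≥8 | 0–2 | Low | Low | Low |
| ≥8 | ≥8 | 3 | High | High | **Low** |

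A and B disagree in 1 of 8 combinations; A and C disagree in 3 of 8. The fifth row conflicts on either reading of the footnote. These are counts of combinations, which are not equally likely, and not shares of patients.

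**Look-back and dated event.** Section 4.1.7 uses 4 weeks; 5.1, 10.1 and footnote 15 use a month. Four weeks is 28 days and a calendar month at most 31, a gap of up to 3 days. The event being dated also varies: footnote 15 dates the hemoglobin test, 10.1 and 4.1.7 date the low hemoglobin, and 5.1 appears to date the transfusion. If test and transfusion fall on either side of the limit, a patient may be covered by one passage and not by another.

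**How many patients.** No passage gives a transfusion frequency. Purely as an illustration, assume that 10–30% of patients are transfused in the prior month, that 20–40% of those are transfused at 8.0–9.9 g/dL, and that 10–30% of those have ECOG 3 or a current hemoglobin below 8 g/dL. With the planned 27 patients:

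- low end: 27 × 0.10 × 0.20 × 0.10 = 0.05 patients
- high end: 27 × 0.30 × 0.40 × 0.30 = 0.97 patients

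The last share includes ECOG 3, so this range matches the literal reading (C). Under the same assumptions the count for reading B would be lower.

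**The case against.** The strongest reply is that footnote 15 is a laboratory note. It hangs on the hematology row, does not mention ECOG, and does not say that the test decides by itself. High risk is defined by ECOG above 2 or hemoglobin below 8 g/dL in 1.1, 5.1 and 10.1, and nothing suspends that definition. Read in place, the footnote says which hemoglobin counts after a transfusion. This stands. A reader might infer that footnote 15 switches off the ECOG criterion, so that ECOG 3 patients are sent to rituximab alone. That needs a strictly literal reading, which the footnote's position in the table does not favor.

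It can also be said that the evident purpose is to stop a transfusion from hiding severe anemia, and that patients with a pre-transfusion value below 8 g/dL within the look-back are high-risk under every passage. That is true, and it confines the problem to transfusions at 8 g/dL or above. Section 5.4.2 generally recommends transfusion below 7 g/dL (on etoposide) or 6 g/dL (rituximab only), which suggests that such transfusions are uncommon. But that guidance covers care during the study and leaves the decision mainly to the provider, so it does not rule them out before enrollment.

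Neither reply removes the conflict. Even as a laboratory note, the footnote replaces the current hemoglobin with the original one, whereas 5.1 and 10.1 keep the current value as a criterion. It also names both groups as possible outcomes, so its text is not limited to adding high-risk patients.

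The look-back difference of up to 3 days is minor and would not justify a change by itself.

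**Conclusion.** The text is wrong as written, within narrow limits. For a patient with ECOG 0 to 2 transfused at 8 g/dL or above whose screening or enrollment hemoglobin is below 8 g/dL, 5.1 and 10.1 give one regimen and footnote 15 the other, with no order of precedence. This rests on the wording alone and holds on both readings of the footnote. A conflict over ECOG 3 arises only on the literal reading.

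The number of patients cannot be computed from the documents. It is probably very few of 27; the illustrative range stays below one patient, but every share in it is assumed. Each affected patient would receive a different regimen depending on the passage followed.

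Two further inferences are not supported. One is that the conflict falls on the sickest transfused patients. Section 1.3 lists ECOG above 2, hemophagocytic syndrome and severe hemolytic anemia as risk factors for early death; it does not list a hemoglobin that falls after transfusion, and the ECOG part depends on the literal reading. The other is that the results by regimen would be blurred. The primary test, the stopping bounds and the survival analyses in sections 10.2 to 10.5 are pooled, and the visible plan has no comparison by regimen. Section 10.6 is redacted and supports neither side.

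**What to change.** Reconcile footnote 15 with 4.1.7, 5.1 and 10.1 so that every combination of pre-transfusion hemoglobin, screening or enrollment hemoglobin and ECOG leads to exactly one risk group. A table like the one above, with a single column of results, would do this.

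- State explicitly whether the ECOG criterion and the current-hemoglobin criterion still apply after a transfusion.
- Give a threshold for low hemoglobin in footnote 15, or refer to the one that applies.
- Use one look-back period and one dated event (test, low value or transfusion) in all four places.

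Which rule applies is for the clinical team to decide. The cost is one footnote and matching wording in three sections. No new data are needed, and the sample size and analyses do not change.

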8.2 Handling of Biospecimens Collected for Correlative Research

Biospecimens collected for this study will be stored in the LCCC Tissue Procurement Facility (TPF), or if needed, in a secure off-site storage facility. All biospecimen samples will be obtained in accordance with procedures outlined in the LCCC 1950 Study Laboratory Manual and stored in containers with controlled access. Each sample will be assigned a unique code number and no identifiable personal health information ill be on the specimen label. Information about the subject's disease will be linked to the specimens stored in the repository database. TPF-associated research staff, LCCC Bioinformatics staff who support the TPF database and the LCCC Data Warehouse, and researchers with IRB-approval for access to PHI for each subject in this study will be able to link specimens to relevant medical information. Some results from laboratory analyses that occurred during the subject's participation in the clinical study may also be included. This information may be important for understanding how the subject's cancer developed and responded to treatment.

Storage Time:

- The biospecimen will be used first and foremost for research purposes outlined within the confines of this protocol. Samples will be discarded/destroyed after relevant data are collected for this study, unless consent was obtained from the subject to use tissue for other research purposes (e.g., TPF consent form was signed by the subject). In this circumstance, there is no time limit on how long biospecimens may be stored.
- The investigator must agree to abide by policies and procedures of the TPF facility and sign a letter of research agreement for ethical and appropriate conduct of their research that utilizes specimens obtained from the TPF facility (e.g., use of leftover specimens will require a protocol outlining the research plan for biospecimen use).

Compliance Statement

Biospecimen collection for this study will be conducted in full accordance to all applicable UNC research policies and procedures and all applicable federal and state laws and regulations, including 45 CFR 46 and the Health Insurance Portability and Accountability Act Privacy Rule. Any episode of noncompliance will be documented.

The investigators will perform the study in accordance with this protocol, will obtain consent and assent (unless a waiver is granted), and will report unexpected problems in accordance with UNC IRB Policies and Procedures and all federal requirements. Collection, recording, and reporting of data will be accurate and will ensure the privacy, health, and welfare of research subjects during and after the study.

8.3 Assessment of Safety

Any subject who receives at least one dose of study therapy on this protocol will be evaluable for toxicity. Each subject will be assessed periodically for the development of any toxicity according to the Time and Events table. Toxicity will be assessed according to the NCI CTCAEv5.0.

8.4 Assessment of Efficacy

All patients with measurable disease who have received at least one dose of treatment and have their disease re-evaluated will be evaluable for assessment of efficacy endpoints. The planned disease measurements are to occur at baseline, day 15, end-of-treatment, and on long-term follow-up.

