3.2 Secondary Endpoints

3.2.1 At study entry, basic demographics and baseline laboratory values will be summarized using descriptive statistics (i.e., means, medians, and variability measures for continuous variable; rates and proportions for binary variables). Screening assessments to be completed within 21 days prior to study enrollment.

3.2.2 Overall survival will be assessed at 12 weeks, one year, and two years from the start of treatment.

3.2.3 Event-free survival will be defined as the rate of refractory disease, relapse (same definition of active disease as in the inclusion criteria in section 4.1), non-Hodgkin lymphoma development or death and will be assessed at 12 weeks, one year, and two years from the start of treatment.

3.2.4 Clinical response rate at end of treatment and 12 weeks from treatment initiation (clinical response defined as resolution of presenting signs/symptoms that defined

the Multicentric Castleman disease (MCD) attack) without relapse at 12 weeks. MCD attack/flare is defined in Section 4.1.1.

3.2.5 Radiologic response rate is the percentage of patients without relapse at end of treatment and 12 weeks from treatment initiation. Chest radiography and abdominal sonography will be used for staging. Per Revised response criteria for gross lymphadenopathy, response will be evaluated via complete survey of lymph nodes with measurements and physical assessment of other palpable masses with measurements.

Response criteria for lymph node response will be as follows: Complete response (CR)- disappearance of all evident disease; Partial response (PR)-at least 50% decrease in target lesions with no increase in non-target lesions, Stable disease (SD)- Neither sufficient shrinkage to qualify for PR nor sufficient increase to qualify for progressive disease (PD); PD- appearance of a new lesion or at least a 50% increase in lesion size.

3.2.6 Additional safety assessment will be graded by CTCAE v 5.0 through 12 weeks from the start of therapy.

3.2.7 Kaposi sarcoma exacerbation will be defined as new symptoms attributed to KS or clinically evident exacerbation of dermatologic or visceral disease. All disease flares will be biopsy confirmed whenever possible.

3.2.8 Quality of life will be assessed by the MCD symptom score, a patient-reported outcomes questionnaire, and PROMIS Global 10, at baseline (week 1), 15 days (week 3), end of treatment (week 5), 12 weeks, 6 months, and 24 months after treatment, and at the time of any relapse.

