A similar strategy for response assessment based on target lesions documented by physical exam alone is currently being utilized at UNC Project Malawi for a clinical trial for lymphoma.

Response criteria for lymph node response will be as follows.

- Complete response (CR): Disappearance of all evident disease. Any pathological lymph node (LN), whether target or non-target, must have decreased to <10mm in diameter. Any non-target lesion evident by chest x-ray or ultrasound must also be documented to have resolved by repeat evaluation.
- Partial response (PR): At least a 50% decrease in SPD of up to six target lesions without any increase in size of non-target lesions.
- Stable disease (SD): Neither sufficient shrinkage to qualify for PR nor sufficient increase to qualify for PD.
- Progressive disease (PD): Appearance of a new lesion(s) >15mm in diameter, at least a 50% increase in SPD of more than one node, OR at least a 50% increase in diameter of a previously identified node >1cm. Given numerous causes of adenopathy in Malawi (particularly among HIV-infected individuals) and in order to exclude alternative non-lymphoma diagnoses, a concerted attempt to re-biopsy at the time of relapse or progression will be made unless patients refuse or the site is not amenable using locally available resources.

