8.4.1 Tumor Measurement

See 7.1.7 for details of tumor measurement and response assessment.

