10.5 Secondary Objectives

10.5.1 To better characterize MCD presentation in Malawi.

Basic demographics and baseline laboratory values will be summarized using descriptive statistics (i.e., means, medians, and variability measures for continuous variable; rates and proportions for binary variables).

10.5.2 To describe the efficacy of the risk-adjusted approach as determined by clinical and radiologic response rates, 90-day, one-year, and two-year EFS and OS.

An event for EFS is either relapse (defined as “MCD attack” in the Inclusion Criteria (section 4.1)), refractory disease, lost-to-follow-up (LTFU), or death. We will consider patients LTFU if they cannot be contacted by phone for three months. Given the high mortality associated with MCD and previously published literature supporting a strong association between LTFU and mortality in SSA, we will consider LTFU as a failure event for both EFS and OS.⁴³ Relapse for purposes of this study will be defined as recurrence of an “MCD attack” (Inclusion Criteria; section 4.1) requiring re-initiation of treatment, with a strong preference for biopsy-proven recurrence whenever possible. We will conduct survival analysis using Kaplan-Meier methods. Radiologic response will be assessed in parallel with clinical response with response criteria defined in section 7.1.7. We will assess the prognostic value of radiologic response for EFS and OS in Cox proportional hazards model.^{10,15,16}

10.5.3 To describe the safety, as determined by the rate of all AEs during a risk-adjusted approach to treatment of MCD in Malawi.

All AEs will be described up to 30 days after final dose of MCD-directed treatment.

10.5.4 To describe the rate of KS exacerbation, as defined by symptomatic or clinical (dermatologic or visceral organ) exacerbation of disease.

The rate of KS exacerbation will be reported as the number of KS cases requiring KS-specific treatment divided by the number of patients with pre-existing KS (as defined by personal history of KS, baseline presence of KS, or KS in lymph node biopsy). This will be estimated along with a 95% confidence interval for the proportion.

10.5.5 To describe the quality of life of patients with MCD before, during and after treatment with a rituximab-based, risk-adjusted treatment approach, as assessed by the MCD symptom score⁴² and PROPr instrument.⁴⁴

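### Section 8.4 removes treated patients who die or are lost before re-evaluation from the response-rate denominator, and no section counts them as non-responders; the likely bias is upward but small

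*Combined protocol and SAP*

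**What the plan says.** All references are to the combined protocol and SAP.

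- **Evaluable set (8.4).** The rule is that patients having "measurable disease who have received at least one dose of treatment and have their disease re-evaluated will be evaluable for assessment of efficacy endpoints". Disease is to be measured at baseline, on day 15, at end of treatment and during long-term follow-up. Section 8.4.1 then adds: "See 7.1.7 for details of tumor measurement and response assessment".
- **Clinical response (3.2.4).** It is assessed at end of treatment and week 12, with "clinical response defined as resolution of presenting signs/symptoms that defined" the MCD attack, and without relapse at week 12. No denominator is given.
- **Radiologic response (3.2.5).** "Radiologic response rate is the percentage of patients without relapse at end of treatment and 12 weeks from treatment initiation". The same item then lists CR, PR, SD and PD. Section 7.1.7 defines these in full; PR, for example, is "At least a 50% decrease in SPD of up to six target lesions without any increase in size of non-target lesions". Neither place has a category for an unassessed patient.
- **Analysis (10.5.2).** The objective reads: "To describe the efficacy of the risk-adjusted approach as determined by clinical and radiologic response rates, 90-day, one-year, and two-year EFS and OS". Radiologic response is to use the 7.1.7 criteria. Death is an event, and "we will consider LTFU as a failure event for both EFS and OS", the reason given being the high mortality of MCD and "previously published literature supporting a strong association between LTFU and mortality in SSA".
- **Withdrawals.** Section 5.9 asks for a complete final evaluation, and footnote 3 of Table 7 for an end-of-treatment visit.
- **Safety (8.3).** Every subject with at least one dose is evaluable for toxicity.

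**The concern.** Being re-evaluated is itself an outcome. A patient who dies in the first or second week, or stops attending without notice, cannot be re-evaluated and so drops out of the response rate altogether. The withdrawal provisions in 5.9 and Table 7 reach only patients who can still attend. The plan's own reasoning in 10.5.2 is that lost patients are mostly failures, so removing them would tend to raise the response rate. In a single-arm trial no comparator absorbs such a shift.

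Two wording problems sit next to this. Read literally, 8.4 applies the measurable-disease condition to every efficacy endpoint, including clinical response, EFS and OS, which does not fit 10.5.2. It would also remove eligible patients who enter with hepatosplenomegaly (4.1.7) and have no superficial measurable node (7.1.7). And 3.2.5 defines radiologic response as absence of relapse, which is a different endpoint from CR or PR: a patient with stable disease could meet the first and not the second.

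**Working it through.** **The plan's own figures.** No sample size or power is stated for response. The 27 comes from the safety test in 10.2, which reproduces: with 24 patients and rejection at 6 or fewer events, the exact probability is 0.096 at a true rate of 40% and 0.811 at 20%, against the stated 0.1 and 80%. 24/(1 − 0.10) = 26.7, rounded up to 27.

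**Does another section rescue the dropped patient?**

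| Section | Counts a never re-evaluated patient as a non-responder? |
|---|---|
| 3.2.4, 3.2.5 | No denominator and no rule for a missing assessment |
| 7.1.7 | CR/PR/SD/PD only |
| 10.5.2 | Failure rule for EFS and OS only |
| 5.9, Table 7 footnote 3 | Reach withdrawn patients who attend, not deaths or silent losses |

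None does, so 8.4 governs.

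**How many patients?** Inputs: 27 enrolled and 10% loss over the toxicity-monitoring period (10.2), taken as 12 weeks to match 3.1; 5% death in the first four weeks on rituximab alone (1.3). Assumptions: events spread evenly, no overlap between deaths and losses.

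- Deaths: 27 × 0.05 = 1.35 over 4 weeks. Losses: 27 × 0.10 = 2.7 over 12 weeks.
- If the day-8 node examination (7.1.4) counts as re-evaluation, the exposed time is one week: 1.35 × 1/4 + 2.7 × 1/12 = 0.56. Per patient 0.5625/27 = 0.0208. P(at least one) = 1 − (1 − 0.0208)^27 = 43%; P(two or more) = 11%.
- If the first re-evaluation is the day-15 measurement named in 8.4, the exposed time is two weeks: 1.35 × 2/4 + 2.7 × 2/12 = 1.125. Per patient 0.0417. P(at least one) = 68%; P(two or more) = 31%.

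**Effect on the rate.** The number of responders is assumed, and the dropped patients are taken as non-responders.

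| Responders | None dropped (/27) | One dropped (/26) | Two dropped (/25) |
|---|---|---|---|
| 15 | 55.6% | 57.7% (+2.1) | 60.0% (+4.4) |
| 20 | 74.1% | 76.9% (+2.8) | 80.0% (+5.9) |
| 24 | 88.9% | 92.3% (+3.4) | 96.0% (+7.1) |

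For scale, the exact 95% CI for 20/27 is 54% to 89%. If the one dropped patient were instead a responder, 20/27 = 74.1% would become 19/26 = 73.1%, so the direction depends on the dropped patients being mostly failures.

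**Radiologic response.** No arithmetic is needed. Section 3.2.5 counts patients without relapse, while 10.5.2 applies the 7.1.7 criteria. CR needs documented disappearance of disease and PR a measured fall in SPD, so the two definitions classify stable disease and unassessed patients differently.

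**The case against.** - **8.4 is prespecified, and an evaluable set is a recognised choice.** True: its three conditions are fixed in advance. But one of them depends on outcome, and the plan pairs it with no all-treated analysis of response. How to score a patient who was re-evaluated once but missed end of treatment or week 12 is also left open.
- **8.4 may be meant for lesion response only.** The pointer in 8.4.1 to 7.1.7 supports this. On that reading clinical response, EFS and OS are untouched, but the gap remains for lesion response, and the text still names efficacy endpoints in general.
- **Early failures are visible elsewhere.** They are: death and loss to follow-up count in EFS and OS, reported at 12 weeks or 90 days. That limits the harm without correcting the response rate.
- **The effect is small beside the confidence interval.** This stands.

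A reader might infer more than the documents support in three ways.

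1. That dead or unassessed patients will be counted as radiologic responders because they are without relapse. Section 10.5.2 applies 7.1.7, under which an unmeasured patient can be neither CR nor PR. This is a conflict between sections, not a settled rule in favour of the loose reading.
2. That the bias could approach 14 points, as in 21/23 = 91.3% against 21/27 = 77.8%. That needs all four or so expected deaths and losses (1.35 + 2.7 = 4.05) to fall before any re-evaluation; even spread puts only 0.56 to 1.1 there.
3. That EFS or OS is biased. Section 10.5.2 has its own failure rule for both; 8.4 only needs its scope corrected.

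**Conclusion.** The point holds for response rates. As written, 8.4 removes treated patients who die or are silently lost before re-evaluation, and nothing scores them as non-responders. The likely bias is upward: 2 to 3 percentage points if one non-responder is dropped and 4 to 7 if two are, with 0.6 to 1.1 such patients expected among 27. Those counts rest on 5% death in four weeks (a figure for rituximab alone, which 1.3 says falls when etoposide is added), 10% loss over 12 weeks, even spread and no overlap. The size in points also rests on assumed responder counts.

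The scope of 8.4 and the wording of 3.2.5 are separate internal conflicts to reconcile. The number of patients without measurable disease, and the direction of any effect from excluding them, cannot be derived from the documents.

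The affected endpoints are secondary and descriptive, with no decision rule, and the primary safety endpoint uses all treated patients. The change is worth making before analysis, but it does not threaten the trial's main conclusion. Confidence is high that the rule is missing and lower on the exact size.

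**What to change.** **8.4 and 10.5.2.** Delete the re-evaluation condition and restrict the measurable-disease condition to lymph-node (SPD) response. Suggested text for both places:

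> Clinical response, EFS and OS include all patients who received at least one dose. Lymph-node response includes all such patients with measurable disease at baseline. A patient with no assessment at a response timepoint (end of treatment, week 12), including because of death, counts as a non-responder at that timepoint. Results in the re-evaluated subset are reported as a sensitivity analysis.

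**3.2.5.** Replace the without-relapse definition by the percentage of patients with CR or PR per 7.1.7, in line with 10.5.2. Chest X-ray and ultrasound are repeated only at end of treatment (7.1.7, Table 7), so full 7.1.7 status cannot be freshly confirmed at week 12 for lesions seen only on imaging. State that week-12 response is judged on lymph-node measurements, with imaging-only non-target lesions carried at their end-of-treatment status.

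**Cost.** A few sentences in three sections and no new data; node measurements are already scheduled at end of treatment and week 12. Reported response rates become slightly less favourable. A visit missed for administrative reasons counts as non-response, which can pull the rate down; the sensitivity analysis shows by how much.
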